Prescription medications for maintenance of stabilized conditions (e.g., hyperlipidemia, thyroid disease, chronic anxiety or depression, birth control, etc.) are permitted if the condition and the dose are stable for three months prior to study participation.

6. Determination of Sample Size

In that accurate assessment of PPA · and NPA · is of utmost importance in this study, the sample size of 275 is based on the expected precision associated with our estimates expressed in terms of confidence interval width and 10% additional patients in order to compensate for 1 interim analysis performed. It is expected that 10% of data will be lost to follow-up or not evaluable resulting in an effective sample size of approximately 248. The precision associated with each estimate is a function of the true unknown

value of the parameter being estimated, and the percentage of delayed diagnoses by the predicate in the case of positive percent agreement and the percentage of negative diagnoses by the predicate in the case of negative percent agreement. For the purpose of our calculations of the expected confidence interval half width, it is assumed that 40% of patients will be delayed by the predicate. A range of possible scenarios for the true value of the parameter were considered for PPA and NPA and calculations of the expected interval half width appear in the table below:

True value	50%	60%	70%	80%	90%
PPA	10.3	10.1	9.5	8.3	6.2

Note that a true value for π_{PPA} or π_{NPA} of 50% represents the worst-case scenario with regards to precision and therefore may be taken as an upper bound of expected accuracy. Calculations reveal that both confidence intervals will have a half width of at most 9.8

7. Statistical Methods

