7.1.3. Analysis Sets

Two analysis sets will be created for study purpose:

1. Full Analysis Set (FAS). FAS includes all enrolled subjects:

- who signed the informed consent and
- who satisfied to the eligibility criteria

FAS will be used for subjects disposition, population description, and for Safety analysis.

2. Per Protocol Analysis set (PPAS): PPAS is a subset of the FAS, restricted to subjects who adhere to the protocol, in terms of SPM and Scintigraphy procedures, and minimal follow-up.

Two subsets of the PPAS - according to follow-up- will be created and used for Performance analysis purpose:

- PPAS1: Subjects who completed the full study follow up to 6 months FU
- PPAS2: Subjects who completed visit 4 with 3 patient management plans- this group will be larger than the above and will have all data for study end points, even though not completed full study flow.

Listing of major protocol deviations to be excluded from the PPAS1 and 2 will be provided by the study team prior to run statistical analysis.

Per protocol Analysis Sets (PPAS1 and PPAS2) will be used for Performance analyses.

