7.4. Handling of Missing Data and Dropouts

No method of imputation will be used for missing data. A summary of missing data will be provided according to the number of subjects, the time points where the data are missing and

clinical center. For each clinical center, number and percent of subjects with no missing data will be presented in tabular form.

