7.7. Treatment Characteristics

Scintigraphy procedure and SPM procedure completions will be evaluated; all event or technical failure occurring during procedures will be described and reported in data-listing.

Patients with medications (Y/N) will be summarized at baseline and at each follow-up ; details on medications will be provided using data-Listing, for each visit.

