7.10. Safety Evaluation

To monitor safety, subjects will be asked at each visit and during telephone contacts about changes in their medical conditions. Adverse events should be assessed in terms of their seriousness, duration, intensity, and relationship to the study device. All anticipated and unanticipated adverse events will be collected. Subjects will be able to contact the investigator at any time during the study if they note any change in their medical condition. The outcome of each adverse event will be observed and documented.

Safety analysis, including adverse events and device deficiencies incidence and description will be run on FAS only.

a. Adverse Events Definitions and Reporting Requirements

An adverse event (AE) is any complaint or untoward medical occurrence that is an unintended disease or injury or untoward clinical sign (including abnormal laboratory findings) in a subject, users or other persons, whether or not related to the investigational medical device. AEs are non device related, non serious medical occurrences.

A Serious adverse event (SAE) is an untoward medical occurrence in a subject that is not related to the investigational device, comparator, or trial procedures, but that meet the criteria of "serious". A Serious Adverse event is one that:

- Led to a death
- Led to a serious deterioration in the health of the subject that:
 - resulted a life-threatening illness or injury;

- resulted in permanent impairment of a body structure or body function and required inpatient hospitalization or prolongation of existing hospitalization;
- resulted in medical or surgical intervention to prevent life threatening illness or permanent impairment to body structure or body function.
 - Led to fetal distress, fetal death, congenital abnormality or birth defect.

An Adverse Device Effect (ADE) is an occurrence related to or caused by the investigational device, procedure or comparator that is not serious.

A Serious Adverse Device Effect (SADE) is an adverse device effect, comparator, or procedure that has resulted in any of the consequences characteristic of a serious adverse event and is serious, but is not unanticipated.

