An Unanticipated Serious Adverse Device Effect (USADE) (also called an unanticipated device effect in per 21 CFR Part 812) is any medical occurrence or unintended disease or injury or serious adverse effect (including abnormal laboratory findings) on health or safety or any life-threatening problem or death caused by, or associated with, a device, if that effect, problem, or death was not previously identified in nature, severity, or degree of incidence in the investigational plan or application, or any other unanticipated serious problem associated with a device that relates to the rights, safety, or welfare of subject.

Adverse events will be collected and documented until the end of the study.

All adverse events will be graded as follows:

- Mild: Sign or symptom, usually transient, requiring no special treatment and generally not interfering with usual activities.
- Moderate: Sign or symptom, which may be ameliorated by simple therapeutic measures, may interfere with usual activity.
- Severe: Sign or symptom that are intense or debilitating and that interfere with usual activities. Recovery is usually aided by therapeutic measures and the discontinuation of the study device

may be required.

The relationship of the adverse event to the study is defined as follows:

- Definitely: an adverse event was shown to be related to the study device
- Probable: an adverse event has a strong temporal relationship to study device, and another etiology is unlikely or significantly less likely.
- Possible: an adverse event has a strong temporal relationship to the study device, and an alternative etiology is equally or less likely compared to the potential relationship to study device.
- Unlikely: an adverse event has little or no temporal relationship to the study device and/or a more likely alternative etiology exists.
- Not assessable: Given the information available, sequence and timing of events, it is unknown or impossible to determine the relationship of the adverse event with the study device.
- None: an adverse event has no temporal relationship to study device or has a much more likely alternative etiology.

b. Device Deficiency

Since device deficiencies are not captured on study eCRF they will not be included in this analysis

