7.12. Changes to Planned Analysis

Per protocol, final statistical analysis was scheduled once N=275 patients were enrolled and completed the study ; due to sponsor decision upon interim analysis primary endpoint results, decision have been taken to early stop the enrollment at N=167 subjects. So, final statistical analysis will be run on N=167 enrolled subjects.

8. Validation Requirements

Original Statistical Programmer performs a visual inspection of the code and output to confirm functionality (Level III as per 056-Wi 181).

9. References

2. De La Loge C, Trudeau E, Marquis P et al. Responsiveness and interpretation of a quality of life questionnaire specific to upper gastrointestinal disorders. Clin Gastroenterol Hepatol. 2004 Sep;2(9):778-86.

10. Statistical Appendices

N/A

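### Section 7.10 promises a device-deficiency incidence that part b withdraws, and no failure or non-evaluable rate with a defined numerator, denominator and confidence interval takes its place

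*SAP*

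**What the plan says.** Section 7.10 states the scope of the safety analysis: "Safety analysis, including adverse events and device deficiencies incidence and description will be run on FAS only". Part b of that section, on device deficiency, then says: "Since device deficiencies are not captured on study eCRF they will not be included in this analysis".

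Section 7.7 deals with how the two tests were carried out. It says "Scintigraphy procedure and SPM procedure completions will be evaluated" and that "all event or technical failure occurring during procedures will be described and reported in data-listing". It does not say which statistic the evaluation of completions will use, which subjects form the denominator, or whether an interval will be given.

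The performance analyses, including the primary one, run on PPAS1 and PPAS2 (Section 7.9). Both are subsets of a per-protocol set that is "restricted to subjects who adhere to the protocol, in terms of SPM and Scintigraphy procedures, and minimal follow-up" (Section 7.1.3). Section 7.4 rules out imputation and plans a tabulation of missing data by number of subjects, time point and center.

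**The concern.** There are two linked problems.

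First, 7.10 and its part b give opposite instructions on the same outcome. A reader of the general sentence would expect an incidence table that, by part b, cannot be produced from the case report form.

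Second, this is a study of a diagnostic device, and how often the device yields no usable answer belongs beside its agreement with the comparator. The SAP conditions agreement on tests that worked and does not pre-specify a rate for those that did not. If SPM tests failed in more than a trivial share of subjects, the agreement figures would describe evaluable tests only and could be read as applying to everyone tested. Section 3 says the trial studies the intended-use population, which makes that reading likely.

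**Working it through.** The main check is a comparison of the text; the arithmetic only illustrates scale.

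**1. The contradiction.** Section 7.10 includes device-deficiency incidence, on the FAS. Section 7.10 part b excludes it because it was not captured. Both are current text in one section, and both cannot be followed.

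**2. Where a failed test goes.**
- *Primary analysis (7.9).* Positive and negative percent agreement (PPA, NPA) are conditional relative frequencies. Each needs a scintigraphy result to assign the denominator and an SPM result to assign the numerator. With no imputation (7.4), a subject lacking either result falls out of the 2×2 table, whichever analysis set is used.
- *Analysis sets (7.1.3).* PPAS2 is described as holding the data for all endpoints, so a subject without an evaluable test does not fit it. The list of excluding deviations is still to be supplied by the study team.
- *Safety (7.10 part b).* Device deficiencies are not analysed.
- *Procedures (7.7).* Completions are evaluated, and failures are described and listed. No rate is defined.
- *Missing data (7.4).* The summary is by subject count, time point and center. It is not by cause or by device.

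So failures are reported in some form, but nowhere as a pre-specified proportion with an interval, separately for each test.

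**3. The only related figure in the SAP.** Section 6 says "It is expected that 10% of data will be lost to follow-up or not evaluable resulting in an effective sample size of approximately 248". This reproduces: 275 × 0.90 = 247.5, or about 248. The 10% combines loss to follow-up with unevaluable data and is not split by cause or by test, so no device-failure rate can be taken from it.

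**4. Illustration of scale.** Section 7.12 says "final statistical analysis will be run on N=167 enrolled subjects". Take n = 167 as the denominator; it is an upper limit for the FAS, which also requires eligibility. The failure counts x are assumed. The exact (Clopper-Pearson) limits are: lower = the 2.5% quantile of Beta(x, n − x + 1), set to 0 when x = 0; upper = the 97.5% quantile of Beta(x + 1, n − x).

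| Assumed failures | Rate | Exact 95% CI |
|---|---|---|
| 0 | 0.0% | 0 to 2.2% |
| 2 | 1.2% | 0.1 to 4.3% |
| 5 | 3.0% | 1.0 to 6.8% |
| 8 | 4.8% | 2.1 to 9.2% |
| 17 | 10.2% | 6.0 to 15.8% |

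The last row is 10% of 167 = 16.7, rounded to 17, as if the whole planned loss were technical failure.

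**5. Effect on agreement.** Let f be the share of subjects with valid scintigraphy whose SPM is not evaluable. If those SPM tests count as non-agreement, overall agreement is multiplied by (1 − f). If all 167 had valid scintigraphy, 8 SPM failures give 159/167 = 0.952 and 17 give 150/167 = 0.898. The same holds for PPA and NPA, with f taken among scintigraphy-positive and scintigraphy-negative subjects respectively.

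**The case against.** The strongest reply is that the SAP is not silent. Section 7.7 plans to evaluate completion of both procedures, and Section 7.2 summarises categorical variables by counts and percentages, so a crude completion proportion could be produced. Section 7.1.1 reports per-protocol subjects as a percentage of the FAS and early withdrawals with reasons, and Section 7.4 tabulates missing data. Part b openly says that deficiencies were not captured, and an analyst would probably let the specific text override the general sentence.

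Much of this stands, and it rules out several stronger readings:

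- *A reader might infer that no failure rate will be reported at all, or that failures will appear only in a listing.* Section 7.7 also provides for an evaluation of completions and a description of failures. What is missing is a defined rate.
- *A reader might treat the technical failures of 7.7 as the device deficiencies of 7.10.* Neither term is defined in the SAP, and 7.7 also covers scintigraphy. The two cannot be equated.
- *A reader might blame the choice of per-protocol sets.* Without imputation, a missing result drops out of PPA and NPA in any set.
- *A reader might take the planned 10% loss as a failure rate and conclude that, for example, 120/150 = 80.0% agreement would really be 120/167 = 71.9%.* The 120 and 150 are hypothetical. The contrast also needs all 17 losses to be SPM failures, whereas the 10% includes loss to follow-up and possibly failed scintigraphy. Counting those as SPM disagreement would penalise the device for something it did not do.

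The reply does not remove the contradiction in 7.10, and it supplies no failure or non-evaluable proportion by test with a stated denominator and interval. It leaves that choice until after the data are known.

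**Conclusion.** The contradiction between 7.10 and its part b is certain. It is also certain that the SAP pre-specifies no failure or non-evaluable rate with a defined numerator, denominator and confidence interval, and that subjects without both results cannot contribute to PPA or NPA. It follows that agreement may look better than among all subjects tested. The documents do not show that it does.

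The size is unknown because the SAP gives no failure count. The illustrative rates of 4.8% (2.1 to 9.2) and 10.2% (6.0 to 15.8) rest on assumed counts of 8 and 17 and on 167 as the denominator. They show that even a modest number of failures would be estimated with enough precision to be worth reporting; they do not estimate what happened. The correction is worth making before the final analysis, but the point does not invalidate the primary analysis.

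**What to change.** 1. In Section 7.10, delete device deficiencies from the sentence on the scope of the safety analysis, so that it agrees with part b. State in the study report that they were not collected as such.

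2. In Section 7.7, add a table of the number and percent of subjects with a technical failure or non-evaluable result. The denominator is the FAS subjects who underwent the test in question. Give SPM and scintigraphy separately, each with an exact 95% CI, and keep the listing as support. Call these technical failures or non-evaluable results, not device deficiencies.

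3. In Section 7.9, add a sensitivity analysis of PPA, NPA and overall agreement among all subjects with a valid scintigraphy result, counting a non-evaluable SPM as non-agreement. Report scintigraphy failures separately and do not score them against SPM.

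The cost is a few lines of SAP text, one table and one additional agreement analysis. Section 7.7 already plans to report failures, so no new data collection should be needed, although the study team must confirm that non-evaluable results can be identified for each test. The downside is a slightly less favourable agreement figure beside the primary result if any SPM tests failed.

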7.11. Health Outcomes Analyses

Health outcomes have been previously described.

7.12. Changes to Planned Analysis

Per protocol, final statistical analysis was scheduled once N=275 patients were enrolled and completed the study ; due to sponsor decision upon interim analysis primary endpoint results, decision have been taken to early stop the enrollment at N=167 subjects. So, final statistical analysis will be run on N=167 enrolled subjects.

8. Validation Requirements

Original Statistical Programmer performs a visual inspection of the code and output to confirm functionality (Level III as per 056-Wi 181).

9. References

2. De La Loge C, Trudeau E, Marquis P et al. Responsiveness and interpretation of a quality of life questionnaire specific to upper gastrointestinal disorders. Clin Gastroenterol Hepatol. 2004 Sep;2(9):778-86.

10. Statistical Appendices

N/A

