7.8. Interim Analyses

One (partial) interim analysis Interim analyses has already been performed (June 2015) on primary endpoint, on N=130 patients. Final analysis will occur on 167 enrolled at the end of the study.

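### Section 6 of the SAP gives two different worst-case precisions (10.3 and at most 9.8), and the final 167 patients do not deliver the 9.8 for PPA

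*SAP*

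**What the plan says.** Section 6 (Determination of Sample Size) rests the planned 275 on interval width. It includes "10% additional patients in order to compensate for 1 interim analysis performed" and allows 10% for loss or unevaluable data, "resulting in an effective sample size of approximately 248". For the widths, "it is assumed that 40% of patients will be delayed by the predicate". The PPA row of its table reads 10.3, 10.1, 9.5, 8.3 and 6.2 points at true values of 50, 60, 70, 80 and 90%. The text below the table says that a true value "of 50% represents the worst-case scenario with regards to precision and therefore may be taken as an upper bound of expected accuracy". It then closes: "Calculations reveal that both confidence intervals will have a half width of at most 9.8".

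Section 7.8 says that an interim analysis "has already been performed (June 2015) on primary endpoint, on N=130 patients", and that "Final analysis will occur on 167 enrolled at the end of the study". Section 7.12 gives the reason: "due to sponsor decision upon interim analysis primary endpoint results, decision have been taken to early stop the enrollment at N=167 subjects".

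Section 7.9 plans Clopper-Pearson 95% intervals for PPA and NPA and runs the primary endpoint on both PPAS1 and PPAS2.

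**The concern.** A maximum cannot be smaller than the worst case it is meant to bound. Section 6 prints 10.3 for the case it calls the worst and then gives 9.8 as the limit. A reader cannot tell which figure the design was meant to achieve.

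The section also speaks in the future tense about intervals that will come from a much smaller trial than the one it describes. Sections 7.8 and 7.12 of the same document fix the final number at 167, and the expected precision is never restated for it. At stake is the stated justification: readers would credit the PPA estimate with a precision that the final sample cannot be expected to give.

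**Working it through.** **Inputs.** From Section 6: 275 planned, 10% loss, 40% delayed, PPA row 10.3/10.1/9.5/8.3/6.2, limit 9.8. From Sections 7.8 and 7.12: 167 enrolled. From Section 7.9: 95% Clopper-Pearson intervals.

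**Formulas.** The Wald half width is 1.96 × √(p(1−p)/n). The expected Clopper-Pearson half width is the sum over x of the binomial probability of x given n and p, times half the exact 95% interval width at x. Here n is the number delayed (for PPA) or not delayed (for NPA) on scintigraphy.

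**Step 1: reproduce the table.** Wald at n = 90 gives 10.33, 10.12, 9.47, 8.26 and 6.20, which matches all five printed values. Searching n = 60 to 129, no other n does. One route to 90 is 275/1.10 = 250, then 250 × 0.9 × 0.4 = 90. That would be the size before the interim addition, but this is an inference.

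**Step 2: reproduce the limit.** Wald at p = 0.5 rounds to 9.8 only for n = 99, 100 or 101 (9.85 at 99, 9.80 at 100). The planned evaluable number fits: 275 × 0.9 = 247.5, and 247.5 × 0.4 = 99. So does 250 × 0.4 = 100, so the basis of 9.8 is not unique. On either basis, 10.3 and 9.8 come from different denominators.

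**Step 3: planned size, planned method.** At n = 99 and p = 0.5 the expected Clopper-Pearson half width is 10.2. It takes 107 delayed patients to bring it to 9.8.

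**Step 4: final size.** With 10% loss, 167 × 0.9 = 150.3, giving about 60 delayed and 90 not delayed. With no loss, 167 gives 67 and 100. Half widths in points at p = 0.5:

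| | n | Wald | Expected Clopper-Pearson |
|---|---|---|---|
| PPA, 10% loss | 60 | 12.65 | 13.1 |
| PPA, no loss | 67 | 12.0 | 12.4 |
| NPA, 10% loss | 90 | 10.3 | 10.7 |
| NPA, no loss | 100 | 9.8 | 10.1 |

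**Step 5: other true values.** Expected Clopper-Pearson half widths with 10% loss:

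| True value | 50% | 60% | 70% | 80% | 90% |
|---|---|---|---|---|---|
| PPA (n = 60) | 13.1 | 12.8 | 12.1 | 10.6 | 8.2 |
| NPA (n = 90) | 10.7 | 10.5 | 9.8 | 8.7 | 6.6 |

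**Step 6: sensitivity to the delayed share.** Taking 30 to 50% delayed (an assumed range) and 0 to 10% loss, the worst-case expected Clopper-Pearson half width runs from 11.1 (n = 84) to 15.1 (n = 45) for PPA. For NPA it runs from 9.3 (n = 117) to 11.7 (n = 75). PPA stays above 9.8 throughout; NPA does not.

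**The case against.** The strongest reply is that Section 6 records how 275 was chosen, and keeping an original rationale is normal. Section 7.12 openly gives the planned number, the final number and the reason for the change, so nobody is misled about the size. Once enrolment has ended, the actual intervals replace any expected width. All of this stands, and it limits the finding to the stated justification. It does not excuse the conflict between 10.3 and 9.8, which was already there at 275. Nor does it explain why a document that fixes the final number at 167 still promises 9.8 without marking the figure as historical.

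It is also fair that planning by Wald and analysing by Clopper-Pearson is common. At the planned size the gap is about 0.3 points (9.85 against 10.2), so this is a minor extra point.

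Two stronger readings are tempting, and the SAP supports neither:

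- **That the stop biased the estimates or spoiled the intervals.** A reader might infer this from a stop made on primary-endpoint results. The SAP gives neither the interim results nor a stopping rule, so the size and direction of any bias cannot be determined. The opposite assurance, that ordinary intervals keep their 95% level, is not supported either. As an illustration, assume a true NPA of 50% and 71 non-delayed patients at the interim, 90 if stopped and 149 if continued. Clopper-Pearson coverage is then 94.5% under a rule that stops when the interim NPA is below 40%. It is 93.9% under a rule that stops when the interim NPA is more than 10 points from 50%. These rules are assumed; the shortfalls are small.
- **That the SAP hides the stop or must adjust for it.** Section 7.12 discloses it. Repeating it beside the PPA and NPA estimates, or splitting interim from later patients, is a reporting option and not the correction of an error.

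**Conclusion.** The point holds as a fault in stated precision and should be fixed. Section 6 is internally inconsistent, with a worst case of 10.3 against a maximum of 9.8. The final sample does not deliver 9.8 for PPA: the worst-case half width is 12.0 to 13.1, which is 2.2 to 3.3 points above the limit, with or without loss and by either method. For NPA the case is weaker. By expected Clopper-Pearson it is 10.1 to 10.7 at 40% delayed, but by Wald with no loss it is exactly 9.8, so that miss depends on the assumed loss.

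The figures rest on the SAP's 40% delayed and on a loss between 0 and 10%. The denominators of 60 and 90 are planning values and correspond to neither PPAS1 nor PPAS2. The PPA conclusion survives a delayed share of 30 to 50%. The table as available shows no NPA row; this may be lost text and is not counted.

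**What to change.** In Section 6:

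1. Mark the 275-patient calculation and the 10% interim addition as the original plan, superseded by the stop at 167 described in Section 7.12.
2. Remove the conflict between 10.3 and 9.8 by stating one denominator and method for that original calculation.
3. Add the expected 95% Clopper-Pearson half widths for 167 enrolled, using the two rows in Step 5 of the working.
4. Label 60 delayed and 90 non-delayed as illustrative under the planning assumptions, and say that the actual PPAS1 and PPAS2 counts will set the final precision of each analysis.

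Make no claim that the ordinary intervals keep, or lose, their level under the stop.

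Optional: a sentence beside the PPA and NPA estimates repeating the disclosure in Section 7.12, and a purely descriptive split of interim and later patients. The later group would be too small to prove or exclude bias. If 130 counts enrolled patients, 37 × 0.9 = 33 leaves about 13 delayed and 20 not delayed; if it counts evaluable patients, 150 − 130 = 20 leaves about 8 and 12.

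The cost is a rewritten paragraph and a stated precision that looks less favourable. The primary method and the computed results do not change.
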